depressive episodes than euthymia. Low levels of pregnenolone compared to controls were also reported in generalized anxiety disorder and social phobia.^{100, 101} A recent paper in *PNAS* reported that a synthetic analogue of pregnenolone that binds specifically to MAP2, had antidepressant effects comparable to standard antidepressants in the forced swim test.^{83, 93, 102} In addition, this pregnenolone-analogue had more persistent effects than fluoxetine in the isolation-rearing model that induces depression-related behaviors such as memory deficits, anxiety, and increased passive coping. Because the social-isolation model is associated with increased alcohol use,¹⁰³ the findings suggest that pregnenolone may decrease alcohol use through actions on microtubules. Even more directly relevant to the current application are the data by the PI's group, discussed above, from two placebo-controlled trials by the PI (Brown) that suggest pregnenolone **may improve cognition.** As discussed above, cognition is frequently impaired in alcohol dependence and BPD or schizoaffective disorder. An older literature suggests cognitive enhancement with pregnenolone. The potential neuroprotective effects of pregnenolone through microtubules in alcohol dependence could be associated with improvement in cognition. Marx et al. found that elevations in pregnenolone in patients with schizophrenia or schizoaffective disorder following adjunctive pregnenolone treatment were correlated with cognitive improvements.⁸⁹

Summary of the two proposed medications: We suggest that citicoline and pregnenolone are both promising medications for alcohol use, *as well as mood and cognition*, in BPD and schizoaffective disorder, bipolar type, which are well tolerated and appear to have positive effects on mood and alcohol use but work through different mechanisms. Therefore, both warrant further investigation.

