3.3.b.9. Management of concomitant psychotropic medications: Treatment of patients with the concurrent diagnosis of a major mental illness in addition to alcohol dependence requires the ability to change dosages, or add and subtract concomitant medications in the interest of participant safety, retention, and generalizability. We elected to allow changes in concomitant medications for psychiatric symptoms when clinically needed. To provide consistency to the medication management, the study physicians will take over the management of these medications and use a modification of a treatment guideline we use in several prior studies (see Human Subjects section Figure 2 for detailed guidelines).

3.3.b.10. *Psychosocial platform for all participants:* All participants will receive Medical Management (MM).¹²⁵ This form of counseling has been empirically tested in combination with medications in the COMBINE study, which is the largest pharmacotherapy trial for alcoholism to date.¹²⁶ MM mimics the medication management frequently used in community settings unlike more elaborate psychosocial interventions. The primary goal of MM is to enhance medication adherence, and it is designed to be used by medically trained clinicians providing pharmacotherapy for alcoholism. MM has been empirically validated as effective when administered in conjunction with medication. MM will be delivered at medication monitoring visits by a trained study clinician. Any unscheduled crisis session or additional contact will be recorded and adjusted for in the data analysis. MM Training and Quality Control: Clinicians will be trained as described in the MM Manual. Compliance with the procedurally specified format will be monitored through supervisory sessions with [name].

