respectively, and the limit of detection was 1 pg for both. With participant consent, DNA will also be obtained for future analysis. Plasma samples for DNA will be coded and sent to UT Southwestern McDermott Center for Human Growth and Development. Samples will have their DNA banked in a secure freezer with coded identification that will not include any personal identifiers such as the subject's name. Samples will begin to be analyzed when 50% (100) have been collected. When candidate genes have been suitably refined, and SNP chips become commercially available, appropriate pathways and candidate genes will be assessed via SNP chips and associated with previously assessed behaviors, personality styles, and/or biologic responses. *The neurosteroid and choline levels are essential as biomarkers and predictor of clinical response, as well as to address exploratory aim 5.*

3.3.c. Statistical Analyses Plan

Randomization: A statistician will randomize participants, stratifying by baseline drinks per drinking day of ≥ 8 and < 8 (based on use patterns in our prior studies).

General Analytic Plan: This is a study utilizing a two-stage adaptive trial design with one planned interim analysis (at end of the first stage). Two stages consist of a treatment selection stage (Stage 1) and a stage of early efficacy confirmation of the selected treatment(s) (Stage 2).¹³¹ In **Stage 1**, participants will be randomized at a 1:1:1 ratio to receive one of the three treatments: placebo, citicoline, and pregnenolone. After 99 participants have completed the duration of treatment (completer, dropout, discontinued) an interim analysis will be performed based on the number of drinks per drinking day (primary outcome measure). Based on the interim analysis, adaptations such as stopping the trial early, re-estimating the sample size, or a different randomization scheme may be applied as recommended by the independent DSMB.

Note that a precision analysis (i.e., a confidence interval approach) will be considered for treatment selection at Stage 1.¹³¹ To evaluate the relative risk of making wrong decision and increase confidence in not making wrong decision at Stage 1, sensitivity analyses based on predictive confidence interval of the true difference, which is calculated using the observed difference, at interim analysis will be conducted for treatment selection. At the end of Stage 1, one of the following decisions will be made based on the following principles:

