- 1. The trial will be stopped if neither active treatment appears to be effective (both active treatment effect sizes are smaller than a minimum clinically important difference, defined as an effect size of 0.25).
- 2. The trial will continue to Stage 2, if there is evidence (based on precision analysis i.e., a smaller interval width) that at least one treatment from the interim analysis at end of Stage 1 is more effective than placebo. If both treatments appear to be effective in Stage 1 then the trial will continue with three-arms. Findings from the interim analysis may result in change in sample size required for achieving statistical

significance at a desired power. At the end of Stage 2, data collected from both stages will be combined for a final analysis. Depending on the results of the interim analysis, blinded sample size re-estimation may be performed per recommendation from the DSMB.

Stage 2 will be a two-arm (assuming that only one promising treatment is retained) randomized study comparing the selected treatments from Stage 1 versus the placebo. At the end of the Stage 2, the selected treatment will be compared with placebo using the number of drinks per drinking day as the primary outcome measure. At each stage, the primary efficacy analysis will be performed based on the intention-to-treat (ITT) population, defined as all randomized participants who have at least one follow-up evaluation regardless of their compliance with the protocol. In case of substantial numbers of protocol violations, a per-protocol analysis may be done to determine whether they influence the conclusions. At end of Stage 2 (or end of trial), a clinical superiority test may be performed after non-inferiority has been established, without paying any statistical penalty.

Sample size re-estimation: Sample size re-estimation will be performed based on the number of drinks per drinking day as the primary outcome measure. Sample size calculations will be performed as follows:¹³²

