At Stage 1, we will recruit 99 subjects (i.e., 33 subjects per arm) with 1:1:1 treatment allocation ratio, which provides clinically meaningful minimum *effect size of 0.25 between each treatment arm and placebo with* a two-sided test at the 5% level of significance. After review of interim data, an additional 100 subjects at 1:1 ratio will be recruited at Stage 2. If the effect size for *both* medications is at least 0.50 at interim analysis then we will have 81.4% power with 66 participants per arm and the study will continue with three treatment arms. To summarize: 1) If neither treatment has an effect size of at least 0.25 at interim analysis then the trial is discontinued. *This effect size was selected because it is a clinically meaningful value. Naltrexone has an average effect size of approximately 0.15-0.20 in clinical trials for alcohol dependence.*¹³³ *Thus, a useful new treatment for alcohol dependence should at least have a larger effect size than the standard treatment. This effect size of 0.25 is also an effect size at interim analysis that provides a reasonable likelihood of a significant difference from placebo at study completion assuming some increase in effect size as more participants are*

enrolled and the variance of the data decreases. 2) If one treatment has an effect size of at least 0.25 then the trial continues dropping the less effective treatment (two-arm study of one medication vs. placebo). 3) If both treatments have an effect size of at least 0.50 then neither treatment is dropped and the trial continues as a three-arm trial (both medications vs. placebo). This assumes that the DSMB assessment determines that the selected treatment(s) has an adequate safety and tolerability profile to continue the trial. We anticipate that the interim analysis will take place at approximately month 26 of the study. As an incentive to enroll quickly and avoid prolonging the study, we will mandate that an interim analysis take place by month 34 even if fewer than 99 participants have been enrolled. All interim analysis decisions will be made in consultation with the NIAAA program official and DSMB.

Statistical Methods:

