The primary analysis is to assess between-group differences in alcohol use measures including drinks per drinking day (primary outcome measure), heavy drinking days, and drinking days using Generalized Estimation Equations (GEEs) analysis with a site effect as a cluster. GEE model has been used in a prescription drug abuse treatment study with multiple site adaptive design (Weiss et al., 2010).¹⁰⁶ Point estimates of the difference in the average of the number of drinks per drinking day between treatment groups and their corresponding 95% confidence intervals will be obtained. A similar analysis will be used to assess exploratory aims 1 (mood), 2 (side effects), and 3 (craving). Length of time in the study in weeks will be compared between groups using Cox proportional hazards regression (SAS Proc PHREG). Assessments only obtained at baseline and weeks 6 and 12 (e.g. GGT, AST, ALT and CDT levels) or baseline and week12 (e.g. cognitive assessments, neurosteroid and choline levels) will be analyzed using analysis of variance (ANOVA). The correlation between the reduction in alcohol use/alcohol craving and reduction in manic and depressive symptoms, and also improvement in cognitive outcomes, will be assessed using Pearson's or Spearman's correlation coefficient. To address exploratory aim 6) "Determine whether changes in alcohol craving, mood or cognition occur before or after changes in alcohol use." a panel model with lagged effects¹³⁴ will be used to analyze 12-week longitudinal data (SAS Proc Panel) in order to explore serial correlations between changes in alcohol use and depressive symptoms or cognitive outcomes with lagged effect (e.g. one week, two week). The panel model will be constructed for each alcohol use, alcohol craving, depressive and manic symptom, and cognitive outcome and test if change in alcohol use follows changes in craving, mood or cognition at subsequent visits and vice versa.

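### The plan promises to adjust for crisis sessions and extra contacts, which arise after randomisation, but does not say whether that adjustment enters the primary or interim model

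*Combined protocol and SAP*

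**What the plan says.** **Contacts.** Section 3.3.b.10 (psychosocial platform) says: "Any unscheduled crisis session or additional contact will be recorded and adjusted for in the data analysis". It does not say which outcome or model is meant, whether contacts enter as a count, as any versus none or as a time-varying term, or whether the adjustment is primary, secondary or a sensitivity analysis.

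**Primary model.** Section 3.3.c, Statistical Methods, analyses drinks per drinking day "using Generalized Estimation Equations (GEEs) analysis with a site effect as a cluster". The reported quantity is "Point estimates of the difference in the average of the number of drinks per drinking day between treatment groups", with a 95% confidence interval. No contact term appears there, elsewhere in 3.3.c, or among the missing-data sensitivity analyses in 3.3.d.

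**Population and interim rules.** The General Analytic Plan says: "At each stage, the primary efficacy analysis will be performed based on the intention-to-treat (ITT) population". The trial stops if "both active treatment effect sizes are smaller than a minimum clinically important difference, defined as an effect size of 0.25". The sample size paragraph adds: "If both treatments have an effect size of at least 0.50 then neither treatment is dropped".

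**Baseline drinking.** Randomisation is done "stratifying by baseline drinks per drinking day of ≥ 8 and < 8", and Table 2 schedules the TLFB at both baseline visits. Statistical Methods names only site for the GEE. Section 3.3.b frames the primary aim as change in alcohol use, but the model description does not say how baseline enters. The ANOVA sentence for laboratory and cognitive outcomes does not say so either.

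**The concern.** Contacts made while a participant is on study drug or placebo come after randomisation. A comparison by assignment should not condition on something that assignment can change. The protocol's rationale (3.1.f) holds that both drugs "appear to have positive effects on mood and alcohol use". Mood and drinking are plausible drivers of crisis contacts, so an effect of treatment on contacts cannot be ruled out. If there is one, a contact-adjusted estimate removes part of the effect or mixes it with unmeasured severity.

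At stake are the final treatment difference and, if the interim analysis uses the same model, the effect sizes compared with 0.25 and 0.50. Those decide whether the trial stops, drops a drug or keeps both.

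The baseline question is separate and smaller. Leaving out a strong predictor that has already been collected does not bias the treatment difference. It can cost precision, and it leaves a modelling choice open until the data are in hand.

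**Working it through.** **1. The plan's own figure.** Inputs from 3.3.c: effect size d = 0.50, 66 per arm, two-sided 5%. Two-sample t-test power (noncentral t, 130 degrees of freedom, noncentrality 0.50/√(2/66)) is 81.35%, which matches the stated 81.4%. That figure is therefore an unadjusted two-arm comparison.

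**2. Contacts in the final model (illustration).** The documents give no contact frequency and no correlation. Assume that drinking alone drives contacts, with within-arm correlation r. Then:
- adjusted effect = d(1 − r²)
- residual SD = √(1 − r²)
- standardised effect = d√(1 − r²)

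| r | adjusted effect, d = 0.50 | standardised | power, 66 per arm |
|---|---|---|---|
| none | 0.500 | 0.500 | 81.4% |
| 0.1 | 0.495 | 0.497 | 81.0% |
| 0.3 | 0.455 | 0.477 | 77.6% |
| 0.5 | 0.375 | 0.433 | 69.5% |

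Under this model a true effect of zero stays at zero.

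**3. Contacts in the interim model (same assumption).** With 33 per arm, SE = √(2/33) = 0.246; normal approximation, one comparison. The plan does not say which SD standardises the interim effect, so both are shown. For threshold T:
- raw SD: Φ{[d(1 − r²) − T] / [0.246√(1 − r²)]}
- residual SD: Φ{[d√(1 − r²) − T] / 0.246}

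| r | true 0.50 reads ≥ 0.50: raw / residual | true 0.30 reads ≥ 0.25: raw / residual |
|---|---|---|
| none | 50.0% | 58.0% |
| 0.1 | 49.2% / 49.6% | 57.6% / 57.8% |
| 0.3 | 42.4% / 46.3% | 53.9% / 55.8% |
| 0.5 | 27.9% / 39.3% | 45.3% / 51.6% |

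**4. A different assumed model.** In a simulation, unmeasured severity drove both contacts and drinking, and treatment lowered the contact rate (log rate ratio −0.3 or −0.7). With no true effect, the adjusted estimate was off by about 0.03 to 0.05 SD while the unadjusted one stayed near zero. With a true effect, about −0.45 SD became −0.42 or −0.40. When treatment did not affect contacts, both estimates were −0.444. The direction and size of any bias therefore depend on the assumptions.

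**5. Baseline covariate (precision only).** Let ρ be the correlation between baseline and one follow-up value; it is not in the documents. Against a follow-up-only analysis the variance ratio is 1 − ρ², and power uses d/√(1 − ρ²):
- ρ = 0.3: variance 9% lower, 0.50/√0.91 = 0.524, power 84.8%
- ρ = 0.5: variance 25% lower, 0.50/√0.75 = 0.577, power 90.9%

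The reference is 81.4%. For a 12-week average with equal correlation between all visits (also assumed), the variance saved is ρ²/[(1 + 11ρ)/12], that is 25% or 46%. The site-clustered GEE was not simulated.

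**6. Effect on the interim rule.** If the effect size were divided by the residual SD after baseline adjustment, a true 0.25 would read 0.25/√(1 − ρ²) = 0.262 or 0.289, and a true 0.50 would read 0.524 or 0.577. The choice of SD needs to be stated.

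**The case against.** The strongest reply is that nothing here contradicts anything. Section 3.3.b.10 speaks of the data analysis in general, not the primary analysis. Statistical Methods gives no exhaustive covariate list, so its silence excludes nothing. A secondary contact-adjusted model would honour both sections. The ITT wording defines who is analysed, not which covariates enter. All of this stands, and it is why the point is an ambiguity. It does not remove the need to settle it: the commitment carries no limit, and Statistical Methods is the only definition of the primary model.

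Second, the bias is hypothetical. It requires that treatment changes contacts and that contacts relate to drinking. The rationale text says nothing about contacts, and participants already have weekly psychiatrist visits and medical management. This stands too. A reader might infer that the primary result will be biased, or that the r = 0.5 figures are an expected loss. The documents support neither: r is assumed, and at r = 0.1 the loss is 0.4 percentage points of power.

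Third, because the primary aim refers to change, baseline may already enter as a change score or a repeated measure, and the precision figures are t-test figures while the plan specifies a GEE clustered on site. Both objections hold. The figures show why naming the covariate is worthwhile; they are not the power of the planned model.

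**Conclusion.** The concern holds as an unreconciled ambiguity. The plan commits to adjusting for events that follow randomisation and leaves open whether the primary and interim models are affected, so analysts could fit different models, each with support in the text. The stronger reading, that the two sections necessarily require different primary models, goes too far.

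If contacts did enter those models, and treatment affects contacts that relate to drinking, the result would not be the effect of assignment. Without an effect of treatment on contacts there is no bias. The documents do not fix the size: under the drinking-driven model the effect ranges from negligible at r = 0.1 to material at r = 0.5, and the interim figures also depend on which SD is used.

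The baseline point is one of precision and prespecification, not bias. The change should be made; confidence is medium.

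**What to change.** 1. Reconcile section 3.3.b.10 with Statistical Methods. State that unscheduled crisis sessions and additional contacts are kept out of the primary and interim efficacy models, are reported by arm, and are used at most in a labelled sensitivity analysis.
2. Separately, name baseline drinks per drinking day and the randomisation stratum (≥ 8 / < 8) as covariates of the primary model, and adjust laboratory and cognitive outcomes for their baseline values.
3. State that the 0.25 and 0.50 interim effect sizes use the unadjusted outcome SD, so that adding baseline does not move the decision rule.

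The cost is SAP wording only. All the data are already scheduled for collection, and no visit, assessment or aspect of care changes.

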- Significant alcohol withdrawal (e.g. delirium tremens) based on clinical judgment. Increases in CIWA-Ar scores will initiate a careful clinical assessment of possible worsening of withdrawal symptoms

Rationale for Protocol Discontinuation Criteria: Discontinuation criteria are designed to ensure the internal validity (e.g. accurate diagnoses) and safety (e.g. acute danger to self or others) of the study.

3.3.b.4. Recruitment and Patient Flow at Referral Sources: Recruitment can be challenging in dual diagnosis studies. By limiting enrollment to the subgroup of people with alcohol dependence who also have BPD or schizoaffective disorder bipolar type, the rate of enrollment is generally not as fast as in studies of patients with alcohol dependence alone. However, in both study sites we have had great success in recruiting this patient population using referral sources we have developed in the communities as well as free and paid advertising. The research team has conducted the largest trials in BPD and substance dependence and have conducted trials that included schizoaffective disorder (bipolar type) in addition to bipolar disorder and substance dependence. These single site studies have enrolled up to 115 participants with BPD and alcohol dependence. Given the inclusion and exclusion criteria in the proposed study both the Dallas and Miami sites conservatively estimate that they can enroll 24 participants each year in the study (48 total). Given these numbers total enrollment will take about 4 years and 2 months.

3.3.b.5. Assessments and Outcome Measures: (see Table 2 for Assessment Schedule) Research coordinators will receive training on the SCID in a 2-day course provided the UT Southwestern Psychiatry Clinical Research Infrastructure (P-CRI) (see resources section for more information on the P-CRI). A half-day reevaluation session will be conducted in years 2, 3, and 4 to maintain diagnostic accuracy. Assessments selected are available and validated in both English and Spanish.

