3.3.b.11. Procedures to Maintain the Double-Blind: Psychiatrists and raters who have contact with the subjects will remain blind in the study. One person each at the Dallas and Miami sites, with no participant contact, will maintain a group assignment list in case of emergency situations where an outside physician or clinical staff needs to break the blind. If the blind needs to be broken during the study (e.g. overdose attempt), these staff members will be available to provide this information to physicians providing emergency care. [name] (DSMB support statistician) and the DSMB members will remain independent of the project team and have access to unblinded information. Raters and all persons with participant contact will be blinded to any changes in the protocol (except study discontinuation) resulting from the interim analysis (e.g. dropping a treatment arm).

3.3.b.12. Data Management: A highly experienced data manager from the UT Southwestern P-CRI (see Resources Section) will set up the database, and monitor and advise the research team throughout the study. The data manager has managed data in much larger multisite research studies. At the beginning of the study, a database format will be designed by the Dallas-based data management team in collaboration with the Miami site. A manual containing that format will be transmitted to Miami. Original data will be maintained at the site of collection (Dallas or Miami). However, de-identified data that will be used in the data analysis (e.g. depressive symptoms, alcohol use) will be stored centrally using the secure electronic REDCap system. These data will be reviewed each week by the Dallas monitor and any errors or inconsistencies will be discussed. A data monitor from both the Dallas and Miami sites will review data charts and corresponding digital database content weekly and provide feedback to the PIs and research staff on data quality and recommend remediation, if necessary. To assure consistency and accuracy between sites, the data monitor from the Dallas site will travel every 6 months to review the data collected at the Miami site. Data will be checked for errors or inconsistencies, extreme values, and missing data which will be discussed and resolved.

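### The primary model carries no site, stratum or baseline-drinking term; adding them is nearly free and sharpens the estimate behind the 0.25 and 0.50 interim rules, mainly through baseline adjustment

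*Combined protocol and SAP*

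**What the plan says.** The randomisation paragraph of section 3.3.c names a single factor: "A statistician will randomize participants, stratifying by baseline drinks per drinking day", split at 8 or more versus fewer than 8. Site is not mentioned there. Section 3.3.b.11 does place an assignment list at each site ("One person each at the Dallas and Miami sites, with no participant contact, will maintain a group assignment list"), but for emergency unblinding; it does not describe stratification by site.

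Under Statistical Methods in section 3.3.c, the alcohol-use outcomes are to be compared "using Generalized Estimation Equations (GEEs) analysis with a site effect as a cluster". This is the only place where site enters the analysis. The text gives no working correlation, small-sample correction or covariate list for this model. Neither the stratification factor nor baseline drinks per drinking day is named as a term.

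Section 3.3.b.4 expects an even split: "both the Dallas and Miami sites conservatively estimate that they can enroll 24 participants each year in the study". For Stage 1, "we will recruit 99 subjects (i.e., 33 subjects per arm) with 1:1:1 treatment allocation ratio". The interim rules then act on observed effect sizes. The trial stops if neither drug reaches 0.25, it continues with one drug if one reaches 0.25, and it keeps both if both reach 0.50. The plan does not say whether that effect size is crude or model-based, or which SD standardises it.

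**The concern.** Decisions that cannot be reversed (stopping the trial, dropping a drug) depend on an estimate from about 33 participants per arm. Section 3.3.c also forces the interim by month 34 even if fewer than 99 have been enrolled. Noise that could be removed from that estimate at no cost is therefore worth removing.

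The model as written leaves three gaps.

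- **Site imbalance.** Allocation does not balance site, and naming site as a GEE cluster does not guarantee that imbalance is removed from the point estimate. Under an independence working correlation the estimate is the crude difference, and the imbalance stays. Under an exchangeable structure by site, most of it goes.
- **Variance.** A robust (sandwich) GEE variance relies on many independent clusters, and here there are two. Clustering on site also leaves open how the weekly Timeline Followback records in Table 2 are correlated within a participant.
- **Unused baseline information.** The plan chose baseline drinking as its stratification factor, yet does not say that the analysis will use the stratum or the continuous baseline value.

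**Working it through.** **Plan's own figure.** Section 3.3.c states 81.4% power at 66 per arm, effect size 0.50, two-sided 5%. A two-sample noncentral t gives 81.35% (normal approximation 81.9%). It reproduces, so the effect size is a mean difference in SD units with no covariate adjustment.

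**Inputs from the plan.** 33 per arm, two sites split about 50:50, cut-offs 0.25 and 0.50.

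**Assumptions (not in the plan).** Site gap D in outcome SD units, ranged from 0.2 to 1.0; baseline-outcome correlation r, ranged from 0.4 to 0.6; one observation per participant; no dropout; normal sampling distribution.

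**Step 1: ordinary sampling error.** SE = sqrt(2/33) = 0.246. A null drug reaches 0.25 with probability P(Z > 0.25/0.246) = 15.5%. By symmetry, a drug with true effect 0.50 falls below 0.25 with the same probability.

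**Step 2: site imbalance, crude or independence-GEE estimate.** The between-arm difference in site share has SD sqrt(2 × 0.5 × 0.5/33) = 0.123. Multiply by D and add in quadrature:

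| Assumed site gap D | Added SD | Total SE | Share of variance | Null drug reaches 0.25 | Null drug reaches 0.50 |
|---|---|---|---|---|---|
| 0 (site balanced) | 0 | 0.246 | 0% | 15.5% | 2.1% |
| 0.2 | 0.025 | 0.247 | 1% | 15.6% | 2.2% |
| 0.5 | 0.062 | 0.254 | 6% | 16.2% | 2.4% |
| 1.0 | 0.123 | 0.275 | 20% | 18.2% | 3.5% |

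**Step 3: does the estimator matter?** In simulation (4,000 runs, three arms of 33, two sites, D = 1.0, allocation not stratified by site, null drug), the SE was 0.276 for the crude difference, 0.249 for a GEE with exchangeable correlation by site, and 0.248 with site as a fixed effect. A site term in the model therefore recovers nearly all of the loss without changing the randomisation.

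**Step 4: baseline adjustment.** Adjusted SE = 0.246 × sqrt(1 − r²).

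- r = 0.4: 0.246 × sqrt(0.84) = 0.226
- r = 0.6: 0.246 × sqrt(0.64) = 0.197

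The chance that a drug with true effect 0.50 falls below 0.25 is P(Z < −0.25/SE): 15.5% unadjusted, 13.4% at r = 0.4, 10.2% at r = 0.6.

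**Step 5: how much does stratifying at 8 drinks already secure?** Take r = 0.5, with a near-median split standing in for the cut at 8. Balancing that split gave a simulated SE of 0.226. Full adjustment gives 0.246 × sqrt(0.75) = 0.213. In variance terms, stratification secures (0.246² − 0.226²)/(0.246² − 0.213²), or roughly 60% of the available gain; the continuous covariate supplies the rest. The corresponding chance of missing 0.25 is 15.5% with neither, 13.4% with stratification alone and about 12% with full adjustment.

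**The case against.** The strongest reply is that the site problem is small and the mechanism uncertain, and most of that stands. Random imbalance adds variance, not bias. At a 0.5 SD site gap it moves a null drug's chance of reaching 0.25 by 0.7 percentage points (16.2% less 15.5%). The dominant weakness is the ordinary sampling error at 33 per arm, which is itself about the size of the 0.25 cut-off, and no site term cures that. The documents give no site difference at all.

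The existing stratum may also absorb part of any gap. When a 0.5 SD site gap was made to act wholly through baseline drinking, with r = 0.5 and the drinking stratum balanced, the interim SE was 0.227 against 0.226 with no gap. Only site differences unrelated to baseline drinking would remain. The interim decision is also not purely mechanical: section 3.3.c adds sensitivity analyses based on predictive confidence intervals, and consultation with the DSMB and the NIAAA program official.

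A reader might infer that chance site imbalance passes directly into the 0.25 and 0.50 decisions, or that leaving site out of the stratification invalidates the interim. The documents do not support either inference. The first needs a crude estimate or an independence working correlation, and the plan specifies neither; the second is out of proportion to the probabilities above.

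The objection does not dispose of the unspecified model: the two-cluster variance, the unaddressed repeated measures within participants, or the absence of the stratification factor and baseline value.

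**Conclusion.** The point holds as a recommended improvement to the primary model. As written, that model uses site only as a cluster, with two clusters, and does not commit to adjusting for the stratum or baseline drinking.

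The site component is negligible to modest: an interim SE between 0.247 and 0.275 against 0.246 for assumed gaps of 0.2 to 1.0 SD, and only if the estimator leaves the imbalance in. The baseline component is larger: an SE of 0.226 to 0.197 for assumed correlations of 0.4 to 0.6, measured against an analysis with neither stratification nor adjustment. Because the trial does stratify at 8 drinks, the further gain from the continuous covariate is smaller than that contrast suggests.

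The site gap and the correlation are assumptions; a different completion pattern or the use of repeated weekly measures would change the figures. The two-cluster variance problem does not depend on either and bears on standard errors, intervals and p-values more than on the point estimate.

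**What to change.** Amend section 3.3.c so that the interim and final primary models:

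1. include site, the drinking stratum (8 or more versus fewer than 8) and continuous baseline drinks per drinking day as fixed effects;
2. cluster on the participant, with a stated working correlation for the weekly measures;
3. supply the effect size for the 0.25 and 0.50 rules, defined as the adjusted treatment difference divided by a named SD (for example the pooled baseline SD or the unadjusted outcome SD, fixed in advance).

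This costs SAP wording only; the baseline values are already collected. If the allocation list is not yet in use, add site as a second stratification factor, giving four strata with permuted blocks, which 199 participants support easily. If the list is already in use, leave it alone: the model terms by themselves recover nearly all of the benefit.
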